Any planned or potential discontinuation of study drug should be discussed with the TIMI Hotline (available 24/7). Note that discontinuation of study intervention does not represent withdrawal from the study. If it is confirmed that the participant will permanently discontinue study intervention following discussion with the TIMI Hotline, an Early Termination visit should be performed, which should include assessments of patient-reported outcomes, physical activity (6MWT), and laboratory assessments. In addition, a follow-up visit (F/U1) should be completed approximately 28 days and another follow-up visit (F/U2) should be completed ideally no more than 94 days for the Main Cohort (Cohort A)/Cohort C/Cohort D, and ideally no more than 75 calendar days for the open-label, PK cohort (Cohort B), after discontinuing study intervention primarily for the purpose of assessing resolution of any treatment-related AEs. See the [SoA](#) for data to be collected at the time of discontinuation of study intervention and follow-up for any further evaluations that need to be completed.

Again, it is important to first contact the TIMI Hotline before classifying a subject as ‘Discontinued from Study Intervention’ and completing an Early Termination visit.

In the event of discontinuation of study intervention, it must be documented on the appropriate CRF/in the medical records whether the participant is discontinuing further receipt of study intervention or also from study procedures, posttreatment study follow-up, and/or future collection of additional information.

Follow-Up:

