At approximately 28 calendar days (F/U1), and again ideally no more than 94 calendar days for the Main Cohort (Cohort A)/Cohort C/Cohort D and ideally no more than 75 calendar days for the open-label, PK cohort (Cohort B) (F/U2) after discontinuation of study intervention, participants should return to undergo review of concomitant treatments, vital signs, and assessment for resolution of any treatment-related AEs. Participants continuing to experience AEs at this point following discontinuation of treatment will continue to be followed at least every 4 weeks until resolution or determination, in the clinical judgment of the investigator, that no further improvement is expected. If the unresolved AE is considered by the investigator as possibly related to or associated with ADA formation, the participant will be asked to return for drug concentration and ADA blood sampling at up to 3-month intervals, until the last follow-up of the AE.

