7.2.1. Withdrawal of Consent

Participants who request to discontinue study intervention will remain in the study and must continue to be followed for protocol-specified follow-up procedures. The only exception to this is when a participant specifically withdraws consent for any further contact with them or persons previously authorized by the participant to provide this information. Participants should notify the investigator in writing of the decision to withdraw consent from future follow-up, whenever possible. The investigator should inform the TIMI Hotline of any potential withdrawal of consent.

A participant may withdraw from the study at any time at their own request. If a participant withdraws from the study, they may request destruction of any remaining samples taken and not tested, and the investigator must document any such requests in the site study records and notify the sponsor accordingly.

If the participant withdraws consent for disclosure of future information, no further evaluations should be performed and no additional data should be collected. The sponsor may retain and continue to use any data collected before such withdrawal of consent. Lack of completion of all or any of the withdrawal/early termination procedures will not be viewed as protocol deviations so long as the participant's safety was preserved.

The withdrawal of consent should be explained in detail in the medical records by the investigator, as to whether the withdrawal is only from further receipt of study intervention or also from study procedures and/or posttreatment study follow-up, and entered on the appropriate CRF page. In the event that vital status (whether the participant is alive or dead) is being measured, publicly available information should be used to determine vital status only as appropriately directed in accordance with local law.

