8.2. Efficacy Assessments (Main Cohort [Cohort A]/Cohort C/Cohort D)

8.2.1. Patient Reported Outcomes

All PRO assessments are completed electronically by study participants at the clinic as per the SoA and Table 5. Every effort should be made to have the study participant complete all PRO assessments before any other clinical assessments that take place at the clinical site. There are no PRO assessments in the open-label, PK cohort.

Additional details are provided in the PRO/eCOA Training Manual.

Table 5. PRO Assessments

PRO Measure	Assessment schedule	Number of Questions	Completion Time
KCCQ-23	SV1, W0 (baseline), W4, W8, W12, W16, W20, W22, or early term.	23	~6 minutes
PROMIS Fatigue 7a ("Past 7 days" recall version)	W0 (baseline), W12, W22, or early term.	7	~2 minutes
PGI-S	W0 (baseline), W4, W8, W12, W16, W20, W22, or early term.	4	~1 minute
PGI-C	W12, W22, or early term.	4	~1 minute

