- **Endpoint:** Change from baseline in KCCQ-23 CSS at Week 22
- **Intercurrent Events:** There are no changes made based on intercurrent events. For participants who discontinue study intervention, receive a prohibited procedure and/or miss a dose or receive an incomplete dose, all observations post-discontinuation, post-procedure or post-missed/incomplete dose will be included in the analysis set.
- **Population-level summary:** Difference in mean change from baseline for the KCCQ-23 CSS at Week 22 between ponsegromab and placebo

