##### 6.1.1.2. Sensitivity/Supplementary Analyses

A sensitivity analysis will be performed on the complete analysis set, as defined in Section 4. The analysis will mirror the main analysis as laid out in Section 6.1.1.1, but will use Estimand 1b (as described in Section 2.2.3).

Additionally, a supplementary analysis will be performed on the censored analysis set, as defined in Section 4. The summaries and analysis will mirror the main analysis as laid out in Section 6.1.1.1, but will be restricted to participants with a KCCQ-23 CSS score at baseline < 75.

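### For participants who permanently stop drug, the Week 22 value behind Estimand 1b is largely unobserved, and its analysis repeats the primary model's missing-at-random assumption

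*SAP*

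**What the plan says.** The primary Estimand 1 is hypothetical. Data after stopping drug, after a prohibited procedure or after a missed or incomplete dose are censored, and missing values are taken as MAR (SAP 2.2.3). Estimand 1b is the counterpart that ignores these events: "all observations post-discontinuation, post-procedure or post-missed/incomplete dose will be included in the analysis set". It is analysed in SAP 6.1.1.2: "A sensitivity analysis will be performed on the complete analysis set, as defined in Section 4". That analysis copies the main one, so the model is the same MMRM. Protocol 9.1.1.1 gives the purpose of such alternative estimands as checking robustness.

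The data come from the protocol's visit schedule. Table 5 lists KCCQ-23 at "SV1, W0 (baseline), W4, W8, W12, W16, W20, W22, or early term", and Table 1 has no KCCQ-23 at Week 24, Week 32 or the flexible PK/PD visit. On permanent discontinuation of drug, Protocol 7.1 says that "an Early Termination visit should be performed, which should include assessments of patient-reported outcomes, physical activity (6MWT), and laboratory assessments". Two follow-up visits come next, at which "participants should return to undergo review of concomitant treatments, vital signs, and assessment for resolution of any treatment-related AEs". On their timing, "another follow-up visit (F/U2) should be completed ideally no more than 94 days for the Main Cohort (Cohort A)/Cohort C/Cohort D". Protocol 7.2.1 keeps these people in the study: "Participants who request to discontinue study intervention will remain in the study and must continue to be followed for protocol-specified follow-up procedures". No section places a Week 22 KCCQ-23 among those procedures.

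**The concern.** An estimand that disregards discontinuation needs the outcome at the target time from people who discontinued. Here the schedule gives permanent stoppers one KCCQ-23 near the time they stop and no later one. Their Week 22 value is then supplied by a model that assumes they would have evolved like comparable participants whose data continue, most of whom are still on drug. That is the assumption already made for Estimand 1.

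At stake is how the supportive result is read. If the two estimates agree, a reader will take this as evidence that the primary result withstands discontinuation, although for this intercurrent event the agreement is largely built in.

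**Working it through.** **1. The plan's own figure.** Protocol 9.5 randomises 380 participants to 300 mg and placebo, 190 per arm, and assumes 15% discontinuation.

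- Completers per arm = n × (1 − d) = 190 × 0.85 = 161.5. The protocol states about 161, so the figure reproduces.
- Discontinuers = 190 × 0.15 = 28.5 per arm, or 380 × 0.15 = 57 in total.

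The protocol does not say whether the 15% is from drug or from study. Treating all 57 as permanent drug stoppers is an assumption.

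**2. Where the Censored and Complete sets can differ for a permanent stopper.** Week 22 is Day 155 with a window of ±2 days, so Days 153 to 157 (Table 1). SAP 4 censors from last dose + 31 days. F/U2 is ideally within 94 days of stopping. Column C counts 94 days from the last dose. Column D counts from the next due dose (last dose + 28 + 94).

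| A. Last dose (day) | B. Censored after day (A + 31) | C. F/U2 by day (A + 94) | D. F/U2 by day (A + 122) |
|---|---|---|---|
| 1 | 32 | 95 | 123 |
| 29 | 60 | 123 | 151 |
| 57 | 88 | 151 | 179 |
| 85 | 116 | 179 | 207 |
| 113 | 144 | 207 | 235 |

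- For every last dose up to Week 16 (Day 113), Week 22 lies after the censoring point. This is where the Complete set should add a value, and none is scheduled.
- Some early stoppers finish follow-up before Day 153. Where F/U2 falls later, it carries no KCCQ-23.
- If the last dose was on its nominal day, an Early Termination visit in the next dosing window (28 ± 3 days) falls 25 to 31 days after it. That score is already in the Censored set, so the Complete set adds nothing for that person. The SAP text available gives no rule for assigning an Early Termination score to an MMRM visit, so its exact contribution cannot be traced further.

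**3. The model.** Estimand 1 is an MMRM on the Censored set, and Estimand 1b is the same MMRM on the Complete set. For the stoppers in step 2, the inputs are the same or nearly so and Week 22 is absent from both.

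**4. The other planned analyses.** The baseline CSS <75 analysis (SAP 6.1.1.2) uses the same MMRM on the Censored set. The Cohorts A+C and A+D models (SAP 5.2, 6.2, 6.3) use Censored sets with a cohort term. All rely on MAR. No delta-adjusted, tipping-point or reference-based analysis of the primary endpoint appears in SAP 5.3, 6.1.1.2 or Appendix 4.

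**5. Exposure to a departure from MAR.** Suppose that stoppers on 300 mg are δ points worse at Week 22 than MAR predicts, that placebo stoppers follow MAR, and that a fraction d of the arm has no Week 22 value. The treatment difference then shifts by d × δ. All δ values are assumed, because the design effect size and SD are redacted.

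| δ (points) | d = 10% | d = 15% | d = 20% | d = 25% |
|---|---|---|---|---|
| 2 | 0.20 | 0.30 | 0.40 | 0.50 |
| 5 | 0.50 | 0.75 | 1.00 | 1.25 |
| 10 | 1.00 | 1.50 | 2.00 | 2.50 |
| 15 | 1.50 | 2.25 | 3.00 | 3.75 |

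**The case against.** The strongest reply is that Estimand 1b covers three intercurrent events and that the gap concerns one. Participants with a prohibited procedure, or a missed or incomplete dose, can stay on the schedule and give a Week 22 KCCQ-23, which the Complete set keeps. This stands, with a limit. Under SAP 4.2, those who resume complete dosing may, after review, have their later data put back into the Censored set, and their Week 22 value is then in both sets.

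SAP 3.2.2 also provides for censoring a Week 22 value after discontinuation where one exists, so the authors expected that some might. That is fair: the documents support the statement that the value is not scheduled, not that it is never collected. Late stoppers may also have an Early Termination visit close to Week 22.

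The MMRM does not ignore a stopper's own history. With an unstructured covariance, a poor score before stopping lowers the implied Week 22 value. Late stoppers may still have drug on board, since the mean unbound half-life is up to 11.1 days (Protocol 2.2.2.2). Both points argue against treating full loss of benefit as the expected case. Neither tests MAR.

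Finally, the 15% may include deaths, withdrawals of consent and losses to follow-up, so 57 is not a count of people who could have been asked at Week 22.

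**Conclusion.** The point holds for permanent discontinuation of drug. For these participants the Week 22 value that Estimand 1b targets is largely unobserved, its analysis fills the gap under the same MAR assumption as the primary analysis, and no planned analysis of the primary endpoint relaxes that assumption. The primary analysis itself stands. What is missing is a test of it.

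A reader might infer that Estimand 1b cannot be estimated at all, or that it is the trial's only robustness check. The documents support neither. Real Week 22 data enter after procedures and some dosing lapses, and other sensitivity analyses are named, although they share MAR. A reader might also take 0.75 points as a known bias. It is an illustration that rests on three assumptions: all of the 15% are permanent drug stoppers, the departure is 5 points, and it occurs in the 300 mg arm only. The conclusion about the estimand does not depend on these figures.

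**What to change.** In SAP 6.1.1.2, add a multiple-imputation analysis of Week 22 KCCQ-23 CSS for permanent stoppers with no Week 22 value, using a delta adjustment taken to a tipping point, a reference-based imputation, or both. Report Estimand 1b with that analysis and not with the MAR MMRM alone. No new data are needed. SAP 5.3.4 and Appendix 4 already set up multiple imputation of KCCQ-23 changes from baseline for the responder endpoints, which can serve as a starting point. The cost is a little more analysis work and possibly a less favourable supportive estimate.

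Collecting KCCQ-23 at the original Week 22 date from consenting stoppers is optional. Questionnaires are completed at the clinic, so early stoppers would need extra visits beyond their current follow-up. It also comes late for Cohort A: SAP 7.2.1 sets the first interim when about 70% of randomised participants have reached Week 22 or discontinued, with a data cut-off of 8 October 2024. Under the planned analyses it would help only the remaining Cohort A participants, because the Cohort C and D efficacy analyses use Censored sets and would discard off-drug values.

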#### 2.2.4. Secondary Estimand(s)

*The secondary estimands are applied to the comparisons between each ponsegromab dose and placebo. Data from the Main Cohort (Cohort A) will be used for comparisons between ponsegromab 300 mg and placebo. Data from the Main Cohort (Cohort A) and Cohort C, combined (ie, Cohort A + Cohort C), will be used for comparisons between ponsegromab 100, 200 and 300 mg and placebo.*

Estimand related to the HF disease-specific health status secondary objective (Main Cohort [Cohort A]  $\pm$  Cohort C):

Estimand 2 will be similar to Estimand 1, except for the following:

- Endpoint: Change from baseline in each of KCCQ-23 CSS\*, OSS, TSS and physical limitation score at Week 22.
- Population-level summary: Difference in mean change from baseline for the KCCQ-23 CSS, OSS, TSS, or physical limitation score at Week 22 between ponsegromab and placebo.

\* Note: For KCCQ-23 CSS, comparisons between ponsegromab 100 or 200 mg and placebo are based on data from the Main Cohort (Cohort A) and Cohort C combined, only.

Estimand related to the HF disease-specific health status (responses as defined by a  $\geq 5$ -point increase from baseline) secondary objective (Main Cohort [Cohort A]  $\pm$  Cohort C):

Estimand 3 will be similar to Estimand 1, except for the following:

- Endpoint: Response as defined by a  $\geq 5$ -point increase in each of KCCQ-23 CSS, OSS, TSS, and physical limitation score at Week 22.
- Population-level summary: Odds ratio for the proportion of study participants with  $\geq 5$ -point increase in KCCQ-23 CSS, OSS, TSS, and physical limitation score at Week 22 between ponsegromab and placebo.

Estimand related to the physical function secondary objective (Main Cohort [Cohort A]  $\pm$  Cohort C):

Estimand 4 will be similar to Estimand 1, except for the following:

- Endpoint: Change from baseline in the 6MWD at Week 22.
- Population-level summary: Difference in mean change from baseline for the 6MWD at Week 22 between ponsegromab and placebo.

Estimand related to the Fatigue secondary objective (Main Cohort [Cohort A]  $\pm$  Cohort C):

Estimand 5 will be similar to Estimand 1, except for the following:

- Endpoint: Change from baseline in PROMIS Fatigue 7a at Week 22.
- Population-level summary: Difference in mean change from baseline for PROMIS Fatigue 7a at Week 22 between ponsegromab and placebo.

Estimands related to the safety and tolerability secondary objective (All Cohorts):

There are no defined estimands for the incidence of treatment-emergent adverse events and treatment-emergent serious adverse events, abnormal laboratory results and vital signs, and these endpoints will be reported using Pfizer data standards as applicable. The Main Cohort (Cohort A) and Cohort C will be reported combined; the open-label, PK cohort (Cohort B) will be reported separately; Cohort D will be reported separately.

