
 To compare the effect of ponsegromab versus placebo on HF disease-specific health status in participants with HF and serum GDF-15 concentrations CCI pg/mL. 	
 Responses as defined by a ≥ 5-point increase from baseline in KCCQ-23 CSS, OSS, TSS, and physical limitation at Week 22. 	
 Estimand 3 (similar to "hypothetical") is the odds ratio between ponsegromab and placebo on the proportion of participants with ≥ 5-point increases from baseline in each of KCCQ-23 CSS, OSS, TSS, and physical limitation score at Week 22, in participants with HF and serum GDF-15 concentrations CCI pg/mL, under the scenario of no discontinuation of study intervention and without the potential confounding effect of prohibited procedures or participants' non-compliance with dosing.

 To compare the effect of ponsegromab versus placebo on the physical function of participants with HF and serum GDF-15 concentrations CCI pg/mL. 	
 Change from baseline in 6MWD at Week 22. 	
 Estimand 4 (similar to "hypothetical") is the difference between ponsegromab and placebo in mean change from baseline in 6MWD at Week 22, in participants with HF and serum GDF-15 concentrations CCI pg/mL, under the scenario of no discontinuation of study intervention and without the potential confounding effect of prohibited procedures or participants' non-compliance with dosing.

 To compare the effect of ponsegromab versus placebo on fatigue reported by participants with HF and serum GDF-15 concentrations CCI pg/mL. 	
 Change from baseline in PROMIS Fatigue 7a at Week 22. 	
 Estimand 5 (similar to "hypothetical") is the difference between ponsegromab and placebo in mean change from baseline in PROMIS Fatigue 7a at Week 22 in participants with HF and serum GDF-15 concentrations CCI pg/mL, under the scenario of no discontinuation of study intervention and without the potential confounding effect of prohibited procedures or participants' non-compliance with dosing.

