### 2.2.3. Primary Estimand(s)

Estimands related to the HF disease-specific health status primary objective (Main Cohort [Cohort A] only):

*Estimand 1 (similar to “hypothetical”) is intended to provide a population level estimate of the treatment effect on the change from baseline in KCCQ-23 CSS for ponesegromab compared with placebo in all evaluable participants in the Main Cohort (Cohort A), under the scenario of no discontinuation of study intervention and without the potential confounding effect of prohibited procedures or participants’ non-compliance with dosing (ie, using the censored analysis set for the Main Cohort (Cohort A) as defined in Section 4).*

- Population: Participants with HF, elevated circulating GDF-15 concentrations and KCCQ-23 CSS <75.
- Endpoint: Change from baseline in KCCQ-23 CSS at Week 22.
- Intercurrent Events:
  - Discontinuation of study intervention: Data collected after a participant has discontinued study intervention will be censored and treated as missing data.

- b. *Prohibited procedures: Data collected after a participant has undergone prohibited procedures, that would modulate the primary endpoint, will be censored and treated as missing data. Any procedures will be reviewed prior to database lock to determine which would be classed as “prohibited” for this estimand.*
- c. *Inadequate compliance: Data collected after a participant has missed a dose, or has received an incomplete dose, will be censored and treated as missing data. For participants who resume (complete) dosing, their subsequent data may be included in the analysis following a review of their compliance prior to database lock.*

*Missing data due to censoring, study withdrawal or other reasons, are assumed to be missing at random in the analysis.*

- *Population-level summary: Difference in mean change from baseline for the KCCQ-23 CSS at Week 22 between ponsegromab and placebo.*

**Estimand 1b** (similar to “treatment policy”) is intended to provide a population level estimate of the treatment effect on the change from baseline in KCCQ-23 CSS for ponsegromab compared with placebo in all evaluable participants in the Main Cohort (Cohort A), regardless of discontinuation of study intervention, dosing compliance or prohibited procedures (ie, using the complete analysis set for the Main Cohort (Cohort A) as defined in Section 4).

- **Population:** Participants with HF, elevated circulating GDF-15 levels and KCCQ-23 CSS <75

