#### **5.2.4. Logistic Regression with multiple imputation**

*The logistic regression model will include baseline score and treatment as fixed terms in the model. Additional terms may be fitted in the model (eg, cohort, baseline LVEF, log GDF-15 concentration from SV1, baseline log NT-proBNP), as appropriate. Missing values (e.g. due to censoring) will be imputed for missing data using a multiple imputation method as described in Section 5.3. Odds (and 90% CIs) and odds ratios versus placebo (and 90% CIs [and p-values, for secondary endpoints]) will be provided. No adjustments will be made for multiplicity.*

Standard SAS output will be provided to support the statistical summary table for the analysis model and multiple imputation approach, but will not be included in the CSR.

Example SAS code is provided in Appendix 4.

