**Example SAS code for Proportion of Responses (with multiple imputation):**

Assume the SAS dataset is in a long format. The variable 'treatment' should be coded similar to 'Placebo', 'Ponsegromab 100 mg', 'Ponsegromab 200 mg', 'Ponsegromab 300 mg', so that 'Placebo' comes first.

NOTE: If a participant discontinues due to death, they should be included in the imputation, but once their value has been imputed then they should be classified as a non responder.

NOTE: cohort will be included only when data from more than one cohort are included.

```
proc sort data=analysis out=analysis_long;
  by subjid time treatment cohort LVEF GDF15 NTproBNP base;
run;

* Create wide dataset for multiple imputation;
proc transpose data= analysis_long out=analysis_wide prefix=wk;
  by subjid treatment cohort LVEF GDF15 NTproBNP base;
  id time;
  var cfb;
run;
```

```
* Perform multiple imputation;
proc mi data=analysis_wide seed=169 nimpute=20 out=analysis_mi;
  class treatment;
  fcs nbiter=10 reg(/details);
  var base treatment cohort LVEF lgGDF15 lgBNP wk4 wk8 wk12 wk16 wk20
      wk22;
run;

* Determine responders and non-responders at Week 22 for all imputed
  datasets;
data analysis_mi_22;
  set analysis_mi;
  if wk22 >= 5 and wk22 ne . then resp = 1;
  if wk22 < 5 and wk22 ne . then resp = 0;
run;

* Create datasets and combine proportions;
proc freq data=analysis_mi_22;
  tables _imputation_* treatment *resp / out=prop_mi outpct;
run;

data prop_mi_0;
  set prop_mi;
  if resp=0;
  keep _imputation_ treatment count;
  rename count=count_0;
run;
data prop_mi_1;
  set prop_mi;
  if resp=1;
  keep _imputation_ treatment count;
  rename count=count_1;
run;
data prop_mi_combined;
  merge prop_mi_0 prop_mi_1;
  by _imputation_ treatment;
  total = count_0 + count_1;
  p = count_1 / total;
  q = count_0 / total;
  se_p = sqrt((p*q)/total);
run;
proc sort data=prop_mi_combined; by treatment _imputation_; run;

proc mianalyze data=prop_mi_combined alpha=0.1;
  by treatment;
  modeleffects p;
  stderr se_p;
  ods output parameterestimates=prop_mi_out;
run;
```

Example SAS code for Logistic Regression Model (with multiple imputation):

The same imputed datasets as produced above for the 'Proportion of Responses' will be utilized. Note: the imputed dataset should be ordered with 'Resp'=1 first to ensure that the odds ratios are for a response = 1 and the reference group is Placebo.

NOTE: cohort will be included only when data from more than one cohort are included.

```

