* Fit logistic regressions to each imputed dataset and combine results;
proc sort data=analysis_mi_22; by _imputation_ treatment descending resp;
run;

proc genmod data=analysis_mi_22 order=internal descending;
  by _imputation_;
  class resp treatment;
  model resp = treatment cohort LVEF lgGDF15 lgBNP base
            / dist=bin link=logit alpha=0.1;
  lsmeans treatment / cl diff alpha=0.1 exp;
  ods output lsmeans=odds_mi diffs=oddsrat_mi;
run;

*Odds ratios;
data oddsrat_mi;
  set oddsrat_mi(where=( _TREATTXT="Placebo" ));
  if TREATTXT = ' Poncegromab 100 mg ' then treatment = 100;
  if TREATTXT = ' Poncegromab 200 mg ' then treatment = 200;
  if TREATTXT = ' Poncegromab 300 mg ' then treatment = 300;
  if treatment = . then delete;
  SE = StdErr;
run;
proc sort data=oddsrat_mi; by treatment _imputation_; run;

proc mianalyze data=oddsrat_mi alpha=0.1;
  by treatment;
  modeleffects estimate;
  stderr SE;
  ods output parameterestimates=OddsRatios_mi_out;
run;

data OddsRatios_mi_out;
  set OddsRatios_mi_out;
  oddsratio = exp(estimate);
  LCLoddsratio = exp(LCLMean);
  UCLoddsratio = exp(UCLMean);
run;
```

```

* Odds;
data odds_mi;
set odds_mi;
  if TREATTXT = 'Placebo' then treatment = 0;
  if TREATTXT = 'Ponsegromab 100 mg ' then treatment = 100;
  if TREATTXT = 'Ponsegromab 200 mg ' then treatment = 200;
  if TREATTXT = 'Ponsegromab 300 mg ' then treatment = 300;
  if treatment = . then delete;
  SE = StdErr;
run;
proc sort data=odds_mi; by treatment _imputation_; run;

proc mianalyze data=odds_mi alpha=0.1;
  by treatment;
  modeleffects estimate;
  stderr SE;
  ods output parameterestimates=Odds_mi_out;
run;

data Odds_mi_out;
  set Odds_mi_out;
  odds = exp(estimate);
  LCLodds = exp(LCLMean);
  UCLodds = exp(UCLMean);
run;

```

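### Estimand 3 is defined as an odds ratio of response proportions, but the plan reports a covariate-conditional odds ratio with crude percentages; in the pooled A + C analysis of 100 mg the two can disagree in direction.

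*SAP*

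**What the plan says.** **Estimand.** Protocol 3.1 describes Estimand 3 as the "odds ratio between ponsegromab and placebo on the proportion of participants with" at least a 5-point increase in each of four KCCQ-23 scores at Week 22. SAP 2.2.4 repeats this as "Population-level summary: Odds ratio for the proportion of study participants with" such an increase. It makes Estimand 3 similar to Estimand 1, which SAP 2.2.3 says is "intended to provide a population level estimate of the treatment effect". Nothing in either definition mentions conditioning on covariates.

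**Odds ratio.** SAP 5.2.4 states: "The logistic regression model will include baseline score and treatment as fixed terms in the model". It continues: "Additional terms may be fitted in the model (eg, cohort, baseline LVEF, log GDF-15 concentration from SV1, baseline log NT-proBNP), as appropriate". The example code in Appendix 4 fits "model resp = treatment cohort LVEF lgGDF15 lgBNP base" and takes odds and odds ratios from "lsmeans treatment / cl diff alpha=0.1 exp". These are logit-scale least-squares means and differences, exponentiated, with no standardisation step. SAP 6.2.2 requires a cohort term when Cohorts A and C are combined.

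**Percentages.** SAP 6.2.2 also reports the percentage responding by treatment after multiple imputation. The code tabulates "tables _imputation_* treatment *resp / out=prop_mi outpct" and divides responders by the arm total, with no adjustment. SAP 5.3.4 uses the same imputed data sets for both outputs, and Protocol 9.3.3 says that proportions, odds and odds ratios will all be provided.

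**Role of A + C.** SAP 5.2 (approach 3) makes the combined A + C data the main analysis for 100 mg and 200 mg.

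**The concern.** An odds ratio for the proportion of responders is formed from two population proportions. The exponentiated coefficient of an adjusted logistic model is a different quantity: it compares participants with the same covariate values. Odds ratios are non-collapsible, so the two differ even under perfect balance, provided that the covariates predict response and treatment has an effect. The estimand as written is then not the quantity estimated. The reported odds and odds ratio will also generally not be reproducible from the percentages reported with them. Because both come from the same imputed data, covariate adjustment causes the gap, not missing-data handling.

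Pooling Cohorts A and C adds a separate problem, which is confounding and not non-collapsibility. The arms draw on the two cohorts in very different shares. The odds ratio adjusts for cohort and the percentages do not. The percentages for 100 mg against placebo can therefore mislead even if no other covariate matters.

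**Working it through.** **Inputs from the documents.** Planned numbers (Protocol 4.1): Cohort A has 190 placebo, 18 at 100 mg, 18 at 200 mg and 190 at 300 mg; Cohort C has 130 at 100 mg and 65 placebo; Cohort D has about 50 and 50. About 161 evaluable per arm for 300 mg and placebo (Protocol 9.5), which agrees with 190 × 0.85 = 161.5. The documents give no response rate, odds ratio or covariate effect for this endpoint, so there is no stated figure to reproduce and the values in steps 1 and 4 are assumptions.

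**1. Conditional to marginal odds ratio.** Assume 40% placebo response, a conditional odds ratio of 1.80, and a normal covariate score with SD s on the logit scale. With φ the standard normal density, choose a so that ∫ expit(a + s·z) φ(z) dz = 0.40. Then p1 = ∫ expit(a + ln 1.80 + s·z) φ(z) dz, and the marginal odds ratio is [p1/(1 − p1)] / (0.40/0.60).

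| s | p1 | marginal OR | conditional OR larger by | placebo odds at mean covariates |
|---|---|---|---|---|
| 0.25 | 54.3% | 1.78 | 0.9% | 0.66 |
| 0.5 | 53.7% | 1.74 | 3.3% | 0.65 |
| 1.0 | 52.0% | 1.63 | 10.7% | 0.61 |

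The placebo odds from the 40% proportion itself are 0.40/0.60 = 0.67.

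**2. Simulation, 161 per arm, 1,000 trials per setting.** With a conditional odds ratio of 2.0 and s = 1.0, the geometric means are 2.05 adjusted, 1.80 crude and 1.79 standardised. With a true odds ratio of 1.0, one-sided 5% rejection is 4.3% to 6.1% over the settings (Monte Carlo SE about 0.7 points). The test keeps its level.

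**3. Cohort weight in the crude A + C percentages.** Share of each arm from Cohort C:
- 100 mg: 130/(18 + 130) = 130/148 = 0.878
- placebo: 65/(190 + 65) = 65/255 = 0.255
- difference: 0.878 − 0.255 = 0.623

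A difference of d points in response between the cohorts therefore enters the crude 100 mg contrast as about 0.62·d. A common 15% discontinuation rate cancels. For A + D the weight is 190/240 − 190/240 = 0.

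**4. Can the direction differ?** Assume placebo response of 45% in A, a within-cohort odds ratio of 1.3, and lower response in C.

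*C lower by 10 points (35%).* Response at 100 mg is 51.5% in A and 41.2% in C.
- Placebo: (190 × 0.45 + 65 × 0.35)/255 = 42.5%
- 100 mg: (18 × 0.515 + 130 × 0.412)/148 = 42.4%

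*C lower by 15 points (30%).* Response at 100 mg is 51.5% in A and 35.8% in C.
- Placebo: (190 × 0.45 + 65 × 0.30)/255 = 41.2%
- 100 mg: (18 × 0.515 + 130 × 0.358)/148 = 37.7%

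The cohort-adjusted odds ratio is 1.3 in both cases. In the second, the percentages favour placebo by 3.5 points.

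**5. The same case, standardised.** Use the planned A + C mix, with 195/611 = 0.319 from C.
- Placebo: 0.681 × 0.45 + 0.319 × 0.30 = 40.2%
- 100 mg: 0.681 × 0.515 + 0.319 × 0.358 = 46.5%

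The gain is 6.3 points with an odds ratio of 1.29, so the percentages and the odds ratio agree again.

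**The case against.** The case for leaving the plan alone has real substance.

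- **The conditional odds ratio is legitimate and prespecified.** Protocol 9.3.1.2 and 9.3.3 name a baseline-adjusted logistic model as the analysis, and its test is valid. Declaring the estimand conditional in SAP 2.2.4, with a footnote, would close the definitional gap. This stands. It would not repair the pooled percentages.
- **The gap may be small.** Only baseline score is mandatory; LVEF, GDF-15 and NT-proBNP are optional in 5.2.4, and the code is offered as a guide. With 161 per arm and 40% v 52%, the SE of the log odds ratio is √[(1/161)(1/0.24 + 1/0.2496)] = 0.225. Even at s = 1.0 the gap is ln(1.80/1.63) = 0.10, under half an SE. This stands.
- **Cohort A already shows a fair contrast for 300 mg.** Allocation to 300 mg and placebo is about 1:1, so the crude percentages there are an unconfounded marginal comparison. Nobody plans to apply the odds ratio to the placebo percentage, and no table shell is given. This stands for Cohort A.
- **No cohort difference is documented.** A and C share eligibility criteria, and reversing a 12-point gain would need about 12/0.623 = 19 points between cohorts. That is fair for a large effect. For a modest one, such as the odds ratio of 1.3 above, about 10 points is enough to erase the contrast.

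A reader might infer that the trial's headline result is inflated. The documents do not support that. This is one of several unranked secondary endpoints, and the primary is a mean difference from an MMRM, which is collapsible.

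**Conclusion.** The mismatch between estimand and estimator is real, and the A + C percentages are the part that most needs changing. The 0.62 weight rests only on planned numbers; the size of any resulting distortion depends on a cohort difference that the documents do not give. The excess of the conditional odds ratio rests on assumed inputs: about 1% to 11% at a conditional odds ratio of 1.80 and 40% placebo response, for a covariate SD of 0.25 to 1.0.

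Two stronger readings should be resisted. The first is that the odds ratio is bound to overstate the effect. The excess holds in expectation, and only with prognostic covariates and a non-null effect; in one trial, chance imbalance can move the adjusted estimate either way. The second is that the A + D outputs share the cohort problem. Allocation is about 1:1 in both, so the planned weight is zero, and those analyses are exploratory with no estimand defined.

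**What to change.** 1. **A + C outputs.** Replace the crude pooled percentages. Within each imputed data set, after deaths are set to non-response, fit the planned logistic model. Predict every participant's response probability under each treatment with cohort and covariates as observed, average to standardised proportions, and pool by Rubin's rules.
2. **Estimand 3, both A alone and A + C.** Report the odds ratio and risk difference of the standardised proportions as the estimate. Use delta-method or bootstrap standard errors, and pool the odds ratio on the log scale.
3. **Conditional odds ratio.** Keep it as supportive and label it conditional on the listed covariates in SAP 2.2.4, 5.2.4 and the table footnotes.
4. **A + D percentages.** No change.

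The cost is SAP wording and modest programming for four scores, with no new data. The reported odds ratio will probably be slightly closer to 1.
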